### 12.3. Laboratory Evaluations

Biochemistry and hematology laboratory tests are scheduled to be collected before the first dose for PK, at Day 1, 8, 15, and 22 for each cycle (frequency could be reduced at later cycles), and at the safety follow-up (30 days after the last dose). Troponin T or I are collected before the first dose for PK, Day 1 and Day 8 of Cycle 1 and Day 1 of Cycle 2 and Cycle 6, and at the safety follow-up. Urinalysis is collected before the first dose for PK, Day 1 of each cycle, and at the safety follow-up.

All continuous laboratory parameters in biochemistry and hematology will be summarized descriptively by actual value at each scheduled visit and the corresponding changes from baseline. The maximum post-baseline and minimum post-baseline (including both scheduled and unscheduled results) will also be provided before the by-visit summary. All parameters will be summarized in SI units.

Shift tables from baseline to visit will be provided for hematology and chemistry parameters to display low, normal, high, and missing values by treatment group in a 3-by-3 contingency table. Denominators for percentages will be the number of subjects with non-missing data at the specific assessment and baseline.

Urinalysis results will only be provided in the listing.

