3 TRIAL DESIGN

3.1 CLINICAL TRIAL OBJECTIVES AND ENDPOINTS

3.1.1 PRIMARY OBJECTIVES AND ENDPOINTS

Primary objectives	Endpoints
To establish the safety profile of SRA737	Safety parameters (referencing National Cancer Institute – Common Terminology Criteria for Adverse Events [NCI-CTCAE] v4.03) including: incidence, seriousness, severity and causality of each AE to SRA737, timing of AE onset, AE duration, and AEs leading to interruption, modification, or discontinuation of study treatment, and primary reason for discontinuation of study treatment if other than disease progression (PD), laboratory (eg, clinical chemistry, hematology, urinalysis) and vital sign data
To determine the MTD with 1 or more schedules of administration of SRA737	The highest dose at which $\leq 33\%$ of subjects have a dose limiting toxicity (DLT) in a cohort of up to 6 subjects
To propose a recommended Phase 2 dose and schedule of SRA737	A safe and well tolerated dose and schedule that provides high exposure, based on all available PK, PDn, and safety parameter data from all cycles of therapy
To evaluate the preliminary efficacy of SRA737 including efficacy in prospectively-selected genetically-defined subjects enrolled into indication-specific expansion cohorts	Objective response rate (ORR) Disease control rate (DCR) Time to response (TTR) Duration of response (DOR) Progression-free survival (PFS) Time to progression (TTP) Overall survival (OS)

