5.4.1 DOSE REDUCTIONS OR DELAYS

Guidelines for dose delays due to AEs are provided in Table 2.

Table 2. Dose Delay and Discontinuation Guidelines

Event	Recommended Action
Grade 3 neutropenia or Grade 3 thrombocytopenia	
Recommend twice weekly monitoring of blood tests if the subject is to continue dosing.
Grade 4 neutropenia or thrombocytopenia or Any non-hematologic \geq Grade 3 SRA737-related toxicity*	
Consider dose interruptionIf toxicities have not resolved to \leq Grade 1 or \leq 1 grade worse than baseline with a dose interruption, continue to delay treatment for up to 4 weeks. If no recovery after 4-week delay, discontinue treatment.
If toxicities have resolved to \leq Grade 1 or \leq 1 grade worse than baseline, treatment may be reinitiated. Consider resumption of treatment at the next lowest dose level for the schedule under investigation or at a reduced dose at an alternative, intermittent schedule.

*Exceptions may include nausea, vomiting or diarrhea lasting < 48 hours, asymptomatic biochemical abnormalities lasting < 5 days, Grade 3 fatigue (unless there was an increase in severity of > 2 grades from baseline), or other event agreed with the Sponsor or Sponsor's designee.

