11.2.2 SAFETY

Safety data will be collected from the date of written informed consent. Safety variables will be summarized by descriptive statistics. Laboratory variables will be described using the NCI-CTCAE v4.03. The MTD for each schedule tested, if reached, and the RP2D and schedule will be described.

Treatment-emergent AEs will be reported for each dose level and coded using a current version of the MedDRA thesaurus, presented as tables of incidence of AEs by body system and by worst severity grade observed. Additional tables will be prepared to summarize incidence of AEs reported as related and unrelated events.

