#### **9.2.4. Analysis Visiting Windows**

No analysis visit window will be defined for safety data or efficacy data except for the tumor marker data. All post-baseline radiological disease assessments will be used for analyses purpose. Nominal clinical visits that are defined in the protocol “Schedule of Event” will be used for summary of safety endpoints. Any unscheduled safety data will not be included in the by-visit summary and will be included in the listings.

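### The protocol commits to describing laboratory data by NCI-CTCAE v4.03, but the SAP plans only low/normal/high shifts by scheduled visit, specifies no graded laboratory output and does not declare the change.

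*SAP*

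**What the plan says.** Protocol 3.1.1 makes the safety profile the first primary objective. It ties the safety endpoint to NCI-CTCAE v4.03 and includes "laboratory (eg, clinical chemistry, hematology, urinalysis) and vital sign data". Protocol 11.2.2 then states the analysis rule: "Laboratory variables will be described using the NCI-CTCAE v4.03".

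SAP 12.3 plans three displays for hematology and biochemistry:

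- Descriptive statistics of values and changes from baseline at each scheduled visit.
- Overall extremes: "The maximum post-baseline and minimum post-baseline (including both scheduled and unscheduled results) will also be provided before the by-visit summary".
- Shifts: "Shift tables from baseline to visit will be provided for hematology and chemistry parameters". These are meant "to display low, normal, high, and missing values by treatment group in a 3-by-3 contingency table".

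On off-schedule samples, SAP 9.2.4 says: "Any unscheduled safety data will not be included in the by-visit summary and will be included in the listings". In SAP 16.1, the two laboratory shift outputs, Tables 14.3.3.2 and 14.3.3.4, are titled by low/normal/high classification.

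**The concern.** A low/normal/high classification records only whether a value is outside the reference range. A CTCAE grade records how far outside. For a drug whose benefit-risk section (Protocol 2.6) names bone marrow as a likely target organ, and whose clinical background (Protocol 2.4) anticipates myelosuppression, the second question matters more.

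The protocol's own rules depend on it. Protocol 3.4 counts Grade 4 neutropenia or thrombocytopenia lasting more than 7 days as a DLT. Table 2 in Protocol 5.4.1 gives different guidance for Grade 3 and Grade 4 cytopenia.

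At stake is one basic safety result: the number of subjects whose laboratory values reached Grade 3, and the number who reached Grade 4. The protocol's commitment would supply it. The SAP does not plan it and does not say it has been given up.

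**Working it through.** No sample size, power or event figure is involved, so the check is a comparison of texts and outputs.

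**Step 1. Is the departure declared?** SAP Section 13 lists five changes from the protocol: disease-type groupings, biomarker endpoints not collected, the exposure-QTc endpoint, the interim reviews, and the alternative response-evaluable population. None concerns laboratory grading.

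**Step 2. Does any planned output grade laboratory values?**

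| Planned output | What it shows | Unscheduled results used? | Subjects at Grade 3 and at Grade 4 by laboratory value? |
|---|---|---|---|
| Tables 14.3.3.1, 14.3.3.3: by-visit rows | Numeric summaries | No | No |
| Same tables: post-baseline minimum and maximum | Numeric summaries | Yes | No |
| Tables 14.3.3.2, 14.3.3.4 | Low/normal/high, baseline to visit | No | No |
| Tables 14.3.2.5, 14.3.2.6 | Subjects with TEAEs of Grade 3 or higher | Not applicable | No: reported AEs only, Grades 3 and 4 pooled |
| Listings 16.2.3.3, 16.2.3.4 | Individual results | Yes | Not specified; would need hand grading and counting |

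**Step 3. What does the shift table do with grades?** Assume every grade of cytopenia is below the laboratory's lower limit of normal. Take two subjects with normal baseline neutrophils, one falling to Grade 1 and the other to Grade 4 at the same visit. Both are counted in the normal-to-low cell. A subject already low at baseline who falls to Grade 4 is counted as low-to-low, which reads as no change. That case is possible: Protocol 4.2.1 admits hemoglobin from 90 g/L and platelets from 100 × 10⁹/L, and if the local lower limits are above those floors, subjects can enter already low.

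**Step 4. Can the count be recovered from the other tables?**

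- *Adding visits.* The shifts run to each visit, not to the worst value. A subject low at three visits appears three times, so even the number ever low cannot be obtained by summing.
- *Post-baseline minima.* SAP 9.2.2 gives mean, standard deviation, median, quartiles and range. A reader who supplied the CTCAE cut-offs could place a cut-off between two quartiles and so bracket the share of subjects below it. A cut-off between Q1 and the median, for example, means roughly 25% to 50%. That is a band, not a count, and it is not linked to baseline grade.
- *TEAE tables.* Protocol 10.1.1 makes a laboratory abnormality an AE only under conditions such as needing intervention, prompting investigation beyond a repeat test, or leading to interruption or discontinuation. A Grade 3 count in a subject who simply continues dosing need not appear. SAP 9.2.3 also assigns Grade 3 to AEs with a missing grade, so AE grade is not a clean proxy for laboratory grade.

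**The case against.** The strongest reply is that severity is reported elsewhere. Post-baseline minima include unscheduled results, so the deepest values appear in a table. Many severe cytopenias would plausibly meet the AE definition and enter the TEAE tables for Grade 3 or higher. DLTs have their own listing (16.2.3.2.5), and individual results are listed. Escalation decisions under Protocol 3.3 rest on cohort review of DLTs and AEs, not on these tables. In addition, Protocol 11.2.2 does not require a laboratory shift table or a worst laboratory grade; its sentence on worst severity concerns AEs.

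Most of this stands. It limits the consequence to reporting and leaves the sponsor some choice over the form of the graded display. It does not remove the conflict: the protocol says CTCAE, and no laboratory output is specified to use it.

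Three stronger readings are tempting but not supported.

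- *That nadirs are lost because unscheduled samples are excluded.* SAP 9.2.4 excludes them from by-visit summaries, but SAP 12.3 includes them in the post-baseline minimum and maximum. Nothing shows that nadirs fall off schedule.
- *That half, later three quarters, of the counts during Grade 3 monitoring are left out.* This sets 8 counts per cycle against 4 scheduled, (8 − 4)/8 = 50%, or against 2 from Cycle 4, (8 − 2)/8 = 75%. Protocol Table 2 says only "Recommend twice weekly monitoring of blood tests if the subject is to continue dosing", with no duration, and note l to the Schedule of Events makes the reduction from Cycle 4 discretionary. These would also be shares of samples, not of nadirs or subjects.
- *That naming four categories for a 3-by-3 table is an error of substance.* The percentages use subjects with non-missing data at both times, which gives a 3-by-3 grid with missing values shown apart. This is a matter of wording.

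**Conclusion.** Wrong as written, in a limited sense: the SAP departs from Protocol 11.2.2 on a component of the primary safety endpoint without declaring it. Both laboratory shift tables are affected, and the result is that no planned table counts subjects by laboratory grade.

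The statement that all grades of cytopenia share one category assumes they all lie below the lower limit of normal; the documents do not reproduce the CTCAE cut-offs. The undeclared departure does not depend on that assumption. A reader might infer that severe cytopenia would be invisible in the study report. The documents do not support that: it would be partly visible through the minima, the TEAE tables and the listings. No numerical size can be attached to what those sources would miss.

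**What to change.** In SAP 12.3, for hematology and biochemistry parameters that CTCAE v4.03 can grade, add to (or substitute in) Tables 14.3.3.2 and 14.3.3.4 a shift from baseline grade to worst post-baseline grade, using scheduled and unscheduled results. Count each subject once per parameter, show Grades 3 and 4 separately, and treat low and high directions separately where both are gradable. State that grades are derived from the laboratory value. Keep low/normal/high for parameters without a grade.

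If the sponsor prefers not to do this, SAP Section 13 should list the departure with a reason. That would make the documents consistent but would not supply the count.

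The cost is programming two tables and a grading derivation from data already collected. No new assessments are needed.

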### 12.4. Serum Tumor Markers

Serum tumor markers are scheduled to be collected before the first dose for PK and at the end of every 4 weeks (+/- 1 week) from Cycle 1 Day 1. Given there are no designated visit for tumor marker collection, the following windowing rules will be applied for summary purpose.

**Table 5: Analysis Visit Windowing Rules for Tumor Markers**

Analysis Visit Name	Target Study Day	Visit Windowing
Baseline	NA	Last assessment prior to first dose
End of Cycle 1	28	21 to 35
End of Cycle 2	56	49 to 63

Analysis Visit Name	Target Study Day	Visit Windowing
End of Cycle n	28 * n	(28 * n - 7) to (28 * n + 7)

Once the analysis visit windowing rules are applied, the result closest to the target study day will be used for summary purpose. If multiple results have the same distance to the target study day the later one will be used. If both results fall on the same day, the one with the larger sequence number will be used.

CEA, PSA, and CA-125 will be summarized descriptively by actual value at each analysis visit and change from baseline at each post-baseline visit. All other tumor markers will be listed only.

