- Urinalysis including glucose, protein and blood: Day 1 of each cycle (may be performed up to 72 hours prior to the first dose of each cycle)

- Blood sample for additional exploratory analyses (such as mutational burden): Cycles 3 and 6, Day 1 predose
- ctDNA for exploratory analyses (from a subset of up to 33 subjects): Cycle 3, Day 1 predose
- CTCs for mCRPC subjects only: End of every 4 weeks \pm 1 week
- Serum tumor markers (if applicable, eg, CA-125 for ovarian cancer, PSA for prostate cancer, CEA for colorectal cancer, CA19-9 for pancreatic cancer, AFP for liver and other cancers, and others as clinically indicated): repeated every 4 weeks \pm 1 week after Cycle 1 Day 1)
- Intensive PK schedule:

Intensive PK Assessments	
Continuous schedule	
• C1 Days 1, 8, and 15: Predose• C1 Day 22: Predose, 1, 2, 4, 6, 8, 12, and 24 hours postdose. For subjects in the Expansion Cohorts, the 12-hour time point may be omitted with Sponsor's approval
	Subsequent cycles, Day 1: Predose
Alternate dosing schedules	
• C1 Day 1: Predose• PK will also be collected on Cycle 1 Day 8 or at a day at the end of the first week's dosing as determined by the Sponsor in consultation with the investigator. 
Time points: Predose, 1, 2, 4, 6, 8, 12, and 24 hours postdose. For subjects in the Expansion Cohorts, the 12-hour time point may be omitted with Sponsor's approval

	Subsequent cycles, Day 1: Predose
Note: The Sponsor may reduce or eliminate the requirement for PK sampling once sufficient data to evaluate the PK of SRA737 have been collected and analyzed. If this occurs, the modified requirements will be documented by an update to the Laboratory Manual.	

- Repeat of clinical assessments (if applicable) performed at baseline: This must be repeated at the end of every 4 weeks (\pm 1 week) after Cycle 1 Day 1. Refer to Section 9.
- Repeat of radiological assessments performed at baseline: Radiological assessments must be repeated every 8 weeks (\pm 1 week) after Cycle 1 Day 1. Subjects with bone metastases being followed by bone scans will have scans every 8 weeks (\pm 1 week) for the first 6 months and then every 16 weeks (\pm 2 weeks) thereafter. Assessment may be discontinued if PD was shown on a previous scan. Refer to Section 9.

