7.3 SAFETY FOLLOW-UP (SFU) VISIT

If a subject discontinues the IMP for any reason, a Safety Follow-up (SFU) visit should be completed. Evaluations at the SFU visit should be performed 30 days \pm 7 days after the last dose of SRA737. If the subject begins a new anticancer treatment within 30 days of the last administration of the IMP, the SFU visit should be performed prior to initiation of the new anticancer treatment, if possible. The following investigations should be performed wherever possible:

- Assessment of AEs (also see Section 7.2.1) and review of concomitant medications
 - Monthly follow up is required for all SAEs and for those AEs considered drug related (highly probable, probable or possible) and present at the SFU visit. Monthly follow-up will continue until the event resolves, returns to baseline, stabilizes, or the subject discontinues from study.
- A symptom-directed physical examination including WHO performance status, temperature, pulse rate, seated BP and weight
- Laboratory tests (blood/urine samples):
 - Hematology tests: CBC with differential count detailed in Section 7.1.2
 - Biochemistry tests: detailed in Section 7.1.2
 - Troponin T or Troponin I: detailed in Section 7.1.2
 - Urinalysis: detailed in Section 7.1.2
 - Blood sample for additional exploratory analyses (such as mutational burden)
 - ctDNA for exploratory analyses (from a subset of up to 33 subjects)
 - CTCs for mCRPC subjects only unless PD was previously documented
 - Serum tumor marker (if applicable, eg, CA-125 for ovarian cancer, PSA for prostate cancer, CEA for colorectal cancer, CA19-9 for pancreatic cancer, AFP for liver and other cancers, and others as clinically indicated must be repeated) unless PD was previously documented
 - Urine or serum pregnancy test
- ECG (locally-read)
- ECHO

- Clinical (if applicable) and radiological assessment of disease, unless PD was indicated on a previous study scan or radiological disease assessments were conducted within the past 6 weeks.
- Compliance: the subject's most recent diary card must be collected and checked for completeness and compliance in taking SRA737.

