7.4 LONG-TERM FOLLOW-UP

For subjects who have not progressed and have not initiated subsequent cancer therapy, clinical, serum and radiological disease assessments will continue to be captured every 16 weeks \pm 2 weeks. Additional contact may be made as requested by the sponsor or the investigator to obtain disease and survival updates on an as-needed basis until the subject discontinues from the study.

The following data will be collected:

- SAEs assessed by the investigator as related to SRA737
- First subsequent cancer therapy (if applicable)
- Laboratory tests (blood samples):
 - Serum tumor markers (if applicable), unless PD was previously documented
 - CTCs (for mCRPC subjects only), unless PD was previously documented
- Clinical disease evaluations, unless PD was previously documented
- Radiographic disease assessments, unless PD was previously documented
- Disease and survival updates, where available

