### 9.3.2. Study Day and Duration

Study day is relative to the start date of the first treatment of the treatment phase. As stated above subjects may have the first dose for intensive PK purpose prior to the first treatment of the treatment phase. In such cases the study day will not align with the very first dose subjects received. It is set up this way to be consistent with the protocol “Day” definition and to avoid confusion in the listings when the study day is used. There is no study Day 0 defined.

- For an assessment that occurred on or after the study treatment:  
Study day = Date of assessment – date of first study treatment in treatment phase + 1
- For an assessment that occurred prior to the study treatment:  
Study day = Date of assessment – date of first study treatment in treatment phase

A duration between any two dates (such as AE duration) expressed in days will be calculated using the following conventions: Duration = later date – earlier date + 1.

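### SAP Table 5 labels tumor-marker results by study day alone, so follow-up values taken off drug can enter End of Cycle rows

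*SAP*

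**What the plan says.** SAP 12.4 describes two kinds of marker draw: one before the first PK dose, and then draws "at the end of every 4 weeks (+/- 1 week) from Cycle 1 Day 1". It gives its reason for windowing as follows: "Given there are no designated visit for tumor marker collection, the following windowing rules will be applied for summary purpose". Table 5 then defines Baseline and End of Cycle n, with target day 28n and a window of 7 days either side. Within a window, "Once the analysis visit windowing rules are applied, the result closest to the target study day will be used for summary purpose"; ties go to the later result. Under SAP 9.3.2, "Study day is relative to the start date of the first treatment of the treatment phase". CEA, PSA and CA-125 are summarized on these analysis visits in Table 14.3.3.5. All marker results go to Listing 16.2.3.6.

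The protocol collects markers at more times than SAP 12.4 names:

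- Section 7.3, SFU visit: "Evaluations at the SFU visit should be performed 30 days" (± 7) after the last dose. Serum markers there "must be repeated) unless PD was previously documented".
- Section 7.4, every 16 weeks ± 2 weeks in long-term follow-up: "Serum tumor markers (if applicable), unless PD was previously documented".
- Section 7.6: the serum-marker row of the Schedule of Events also carries a follow-up entry, with a footnote ending disease assessments at progression or new anticancer therapy.

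**The concern.** The rule looks only at the calendar. It does not ask whether the subject was still taking SRA737, had started the cycle named in the row, or was attending an SFU or long-term visit. The stated reason for windowing, that no designated marker visit exists, holds for the 4-weekly draws but not for the SFU visit.

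The neighbouring SAP sections on laboratory tests, vital signs and ECG (12.3, 12.5, 12.6) each name the safety follow-up as a collection point. SAP 9.2.4 summarizes safety data by nominal protocol visit, so follow-up values there stay under their own visit. Tumor markers are the one exception to nominal visits, and 12.4 leaves the follow-up draws out. SAP 13, which lists departures from the protocol, does not mention this.

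At stake is how Table 14.3.3.5 is read. A reader will take an End of Cycle row as marker change up to that point of treatment. If the row also holds values taken about a month, or several months, after the drug was stopped, it describes neither the treatment period nor the follow-up period. Later rows will have fewer subjects, and each expansion cohort plans only about 20, so a few such values could move a median.

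**Working it through.** **Inputs**

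- Window: 28n − 7 to 28n + 7 (SAP Table 5).
- Day 1 is the first treatment-phase dose (SAP 9.3.2); cycles last 28 days.
- On-treatment draws: every 4 weeks ± 1 week (SAP 12.4; Protocol 7.2.2 and 7.6).
- SFU: last dose + 23 to + 37 days, nominal + 30 (Protocol 7.3).
- Long-term: every 112 ± 14 days (Protocol 7.4, which gives no anchor date).

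**1. Reproduce Table 5.** n = 1 gives Days 21–35 and n = 2 gives Days 49–63, as printed. n = 3 gives Days 77–91. Each window covers 15 of 28 days, leaving 13 uncovered (for example Days 36–48).

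**2. On-schedule treatment draws.** With target day 28n, all 15 allowed days lie in the window. If 4 weeks after Cycle 1 Day 1 is read as Day 28n + 1, 14 of 15 do; only Day 28n + 8 misses.

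**3. SFU after a last dose on Day 56.** The nominal visit is Day 56 + 30 = 86, inside 77–91, so it is labelled End of Cycle 3. Cycle 3 was never started. The allowed days are 79–93: Days 79–91 (13 days) map to End of Cycle 3, and Days 92–93 map to nothing.

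**4. Any last dose on Day 28n.** The SFU range is 28n + 23 to 28n + 37. The next window is 28(n + 1) − 7 to 28(n + 1) + 7, that is 28n + 21 to 28n + 35. The overlap is 28n + 23 to 28n + 35, or 13 of 15 days (87%).

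**5. Other stopping days.** Assume, for illustration, that the last-dose day is spread evenly over the 28-day cycle and the SFU day evenly over its 15 allowed days. That gives 28 × 15 = 420 combinations. Of these, 225 (53.6%, which is just 15/28) get a cycle label: 78 for the cycle of the last dose and 147 for the next one (147/225 = 65%). The other 195 (46.4%) get none.

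**6. Long-term samples after a last dose on Day 56.**

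| Anchor | Nominal day | Label (window) | Allowed days given a label |
|---|---|---|---|
| Last dose, Day 56 | 56 + 112 = 168 | End of Cycle 6 (161–175) | 15 of 29 |
| SFU, Day 86 | 86 + 112 = 198 | End of Cycle 7 (189–203) | 15 of 29 |

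**7. Where the windows are used.** Only in Table 14.3.3.5; SAP Tables 6 and 7 list no other marker table or figure. ORR, DCR, TTP and PFS (SAP 11.1 to 11.3) rest on RECIST assessments and do not pass through Table 5. PSA for mCRPC response review is presented in listings (SAP 11.1.6).

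**The case against.** The best defence is that Table 5 was meant only for the 4-weekly draws. SAP 12.4 mentions only those, windows them because they lack a designated visit, and the SFU is a designated visit in the Schedule of Events. On that view the SAP is merely silent about follow-up samples. That may well be the intention, but the text does not say it. SAP 9.2.4 takes tumor-marker data out of nominal-visit handling without limiting the exemption to treatment draws, and Table 5 has no exclusion. A programmer following the text would label the Day 86 sample End of Cycle 3.

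Several points on the other side do stand, and they rule out stronger readings:

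- A reader might infer that every post-baseline sample receives a cycle label. It does not; samples outside the windows receive none.
- A reader might infer that the 13-day gaps lose treatment data. The windows equal the protocol's collection tolerance, so on-schedule draws are kept apart from the one-day edge under one reading. Off-schedule values leave the summary but remain in Listing 16.2.3.6.
- A reader might infer that a large share of a row is off drug. The documents give no count. Treatment normally continues to progression, and follow-up markers are not drawn once progression is documented, so such samples come only from subjects who stop without it. Step 5 describes possible days, not the composition of a row.
- The SAP never calls the rows on-treatment. That meaning comes from the cycle label.
- The table is descriptive, and no endpoint or dose decision is tied to it.

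**Conclusion.** The point holds in a limited form. As written, Table 5 admits off-drug SFU and long-term values to End of Cycle rows whenever the study day fits, including rows for cycles the subject never started. For a last dose at the end of a 28-day cycle this is the usual result: the nominal SFU day always falls in the next window, as do 13 of the 15 allowed days. For other stopping days the outcome depends on the day; the average of 53.6% rests on the even-spread assumption.

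The rule is wrong as written, but its impact is low. It affects one descriptive table, the number of affected samples cannot be derived from the documents, and the RECIST endpoints are untouched. The documents do not support a claim of material distortion, or of loss of on-schedule data.

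**What to change.** In SAP 12.4 and Table 5:

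1. Assign a sample to End of Cycle n only if the subject received study drug in cycle n, the sample is not an SFU or long-term follow-up sample, and it precedes any new anticancer therapy.
2. Add a separate Safety Follow-up row for SFU samples.
3. Keep long-term follow-up samples in Listing 16.2.3.6 only, and say so.
4. Correct the statement that no designated visit exists, so that it refers to the 4-weekly draws alone.

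Keep the ± 7 day windows, since they match the collection tolerance. Tying the rule to the cycle received, rather than to a fixed number of days after the last dose, matters because Protocol 5.2 allows intermittent schedules. With one week of dosing and three weeks off, the last dose of a cycle falls on its day 7, and the scheduled day-28 sample comes 21 days later. A short cut-off after the last dose would wrongly remove it.

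The cost is a few sentences in the SAP, one extra derivation, and slightly fewer values in the late-cycle rows.
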